6.3 Conventional AF Ablation

Patients randomised to the conventional AF Ablation arm will undergo the conventional Cryoablation procedure. This arm will be used as a second control arm to compare the differences in impact on healthcare resources, complication rates and clinical outcomes between conventional ablation and AVATAR-protocol ablation.

Anticoagulation regime will be physician discretion according to established HRS/ESC guidelines guided by CHADS-VASC scoring system. Patients on anticoagulation may follow a continuous, bridging or without anticoagulation as per local protocol.

The procedure is performed under sedation or general anaesthetic according to local preference. TOE is performed according to local protocols. Femoral sheaths placed in the right

femoral vein (ultrasound guidance allowed). A single or double transeptal puncture may be done guided by TOE, aortic pigtail, ICE or CS catheter guidance. Pulmonary venography taken. The sheath is exchanged for a Cryosheath or other suitable large sheath and an Arctic Front Advance balloon is used to occlude the PV to Grade 3/4 and deliver 2 x 3min cryoablations to each vein. Phrenic nerve monitoring can be according to local protocol.

The PV will be mapped using a circular mapping catheter of the operators choice and the number of veins isolated with this approach documented. PV isolation is completed with either repeat cryoballoon, deflectable cryotherapy catheter or radiofrequency catheter. The catheters used and outcomes documented.

The patient is monitored overnight and should have an Hb, groin and echo (handheld with documentation sufficient) check prior to discharge.

All medication is continued for 4 weeks post-ablation and then all agents being used for anti-arrhythmic effect are stopped.

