11.2 Data Analysis

Primary outcome: Failure is counted when a patient experiences any hospital episode related to treatment for atrial arrhythmia. Patients are censored from their treatment group when they switch to a treatment other than that to which they were originally assigned or when they leave their treatment group without having experienced a hospital episode.

Data will be analyzed using the intention-to-treat principle and a p value of 0.05 or less will be considered significant. Primary outcome will be analysed using Kaplan-Meier statistics and differences will be tested using log-rank test and proportional hazards models. Other outcomes will be compared using t-test for continuous and Chi-square test or Fisher exact test for categorical variables and the appropriate generalized linear model will be used.

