5.5. Sample Size

In this time-to-event study of hospital episodes, required sample numbers have been estimated using the log-rank test under the Freedman method based on the occurrence of first event during the 12-month follow-up period. The null hypothesis is that there is no difference in the distributions. Adopting a conservative approach, an initial two-sided alpha of 0.05 is chosen, given the need to allow for the inherent multiple testing between the three arms of the study, the conservative Bonferroni correction is applied and the alpha value used in the power calculations is reduced to 0.025.

Estimating the proportion experiencing a hospital episode in the follow-up period in the anti-arrhythmic arm as 0.63 and the corresponding proportion in the AVATAR ablation arm as 0.40, assuming the occurrence of 103 events, with 100 evaluable patients in each of the two treatment arms yields a power of 0.80. A similar power is obtained for the comparison of the AVATAR ablation arm (0.40) and the conventional AF ablation arm (0.20).

A sensitivity analysis indicates that these sample size estimates are reasonable. It is anticipated that the loss to follow-up will be small, approximately 7%. Consequently, 321 patients will be randomised in a 1:1:1 manner to a treatment strategy of either AVATAR protocol ablation, anti-arrhythmic therapy or conventional AF ablation and followed-up for 1 year.

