7.3. Safety and Efficacy Variables

The following information will be recorded and reported to demonstrate treatment safety and efficacy:

- Vital Signs (variables including; weight, blood pressure, pulse, body temp)
- Physical Examination
- Patient Health Questionnaires
 - Quality of Life (QoL)
 - Atrial Fibrillation Effect on QualiTy-of-life (AFEQT)
 - Telephone Follow-up
- CHADSVASC score
- ECG (variables including; ventricular rate, PR & QRS interval)
- Concomitant Medications
- Pulmonary Vein Isolation Measurements of Ablation Treatments (variables including; total duration of freeze, number of applications, Grade 4 occlusions, lowest temperature)
- Protocol Deviations and Violations
- Adverse and Serious Adverse Events

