8.4. Safety Variable Analysis

Adverse events will be summarised by treatment and severity. A separate table summarising adverse events and their relationship to study treatment will also be produced.

Serious adverse events will be listed and summarised by site, category and treatment. A separate table summarising serious adverse events and their relationship to study treatment will also be produced.

All safety variables will be summarized in the form of frequency tables for categorical variables or descriptive statistics for continuous variables. Quality-of-Life (QoL) questionnaire results will be summarised by Health State Score. Atrial Fibrillation Effect on QualiTy-of-life (AFEQT) questionnaire results will be summarised by both overall AFEQT score and subscale score derived using the formulae stated within the AFEQT Questionnaire Instruction and Scoring Manual

REFERENCES

If it is deemed appropriate, treatment effect will be assessed via t-test for continuous variables and Chi-square test or Fisher exact test for categorical variables (with the appropriate generalized linear model being used). Models containing one or more of the following covariates may also be assessed if deemed necessary: site, weight, hypertension, number of anti-arrhythmics taken by patient prior to 1st intervention. A p-value of 0.025 or less will be considered significant. Any testing for treatment effect will be carried out between AVATAR-AF Ablation and the Anti-Arrhythmic drug treatment arm in order to investigate the primary objective. The secondary objective will be assessed by testing AVATAR-AF Ablation against the Conventional Ablation arm.

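### Adverse-event and SAE comparisons take over the 0.025 efficacy threshold and have no between-arm estimate or confidence interval

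*SAP*

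**What the plan says.** SAP 7.3 introduces a mixed list, including AEs, SAEs, vital signs, ECG and questionnaires, with the words "The following information will be recorded and reported to demonstrate treatment safety and efficacy".

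SAP 8.4 then summarises AEs by treatment and severity and by relationship to treatment, and lists and tabulates SAEs. Testing is conditional on being thought appropriate. In that case "treatment effect will be assessed via t-test for continuous variables and Chi-square test or Fisher exact test for categorical variables", with a generalized linear model whose link, effect measure and interval are not named. The decision rule is "A p-value of 0.025 or less will be considered significant". The pairs are AVATAR v drugs and AVATAR v conventional ablation.

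The origin of 0.025 is SAP 5.5 (same text in Protocol 11.1): "an initial two-sided alpha of 0.05 is chosen", and after a Bonferroni correction "the alpha value used in the power calculations is reduced to 0.025". That calculation concerns hospital episodes only. The v1.1 entry in the SAP revision history explains the 8.4 edit by pointing back to the primary-analysis edits. Protocol 11.2 has a different general rule: "a p value of 0.05 or less will be considered significant".

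Shells 7.1, 7.2 and 7.4 hold counts by arm, and 7.3 is a listing. None has a column for a difference, a ratio or an interval. By contrast, SAP 8.3 analyses complications and death or stroke by log-rank and Cox models, and Tables 5.6 and 5.3 provide a hazard ratio with a 95% CI for both comparisons.

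**The concern.** A Bonferroni split protects against a false claim of benefit when there are two chances to make one. For harms the costly error is usually the opposite: failing to notice a real excess. Halving alpha makes that error more likely, and nothing in the SAP argues that harms need this protection.

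The second part is what the reader of the report would see. If an AE or SAE comparison is made and gives p > 0.025, the planned tables show counts and no interval, so they do not show how large an excess the data still allow. The trial's case for day-case ablation without mapping includes not worsening outcome for the patient (Protocol 1.1), so the range of excess harm compatible with the data is a question readers will ask.

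**Working it through.** **1. The plan's own figure.** The documents state no power or precision for safety. The only stated power is for the primary endpoint: "assuming the occurrence of 103 events, with 100 evaluable patients in each of the two treatment arms yields a power of 0.80".
- Hazard ratio = ln(1 − 0.40)/ln(1 − 0.63) = 0.514.
- Freedman: √103 × (1 − 0.514)/(1 + 0.514) = 3.260. Subtracting z = 2.241 (two-sided 0.025) leaves 1.018, so power is 0.846.
- The stated 0.80 is therefore slightly low at alpha 0.025. This has no bearing on the safety point.

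**2. Inputs for the safety check.**
- Patients per arm: 321/3 = 107 (SAP 5.5).
- Threshold: 0.025 (SAP 8.4), compared with 0.05 (Protocol 11.2). Two-sided tests are assumed, as in SAP 5.5.
- Event rates: none given. A range is assumed, with the rate doubled in one arm.

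**3. Normal approximation for 5% v 10%.**
- Null SE = √(2 × 0.075 × 0.925/107) = 0.0360.
- Alternative SE = √((0.05 × 0.95 + 0.10 × 0.90)/107) = 0.0358.
- At 0.025: (0.05 − 2.241 × 0.0360)/0.0358 = −0.86, so power is 0.196 and the miss rate 80%.
- At 0.05, with z = 1.960, the miss rate is 72%.

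**4. Exact results.** All pairs of binomial counts at 107 per arm were enumerated. The table gives the probability that a true doubling does not reach the threshold.

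| Assumed rates | 0.025, chi-square | 0.025, Fisher | 0.05, chi-square | 0.05, Fisher |
|---|---|---|---|---|
| 2% v 4% | 93% | 98% | 88% | 95% |
| 5% v 10% | 81% | 87% | 71% | 79% |
| 10% v 20% | 57% | 64% | 45% | 53% |
| 15% v 30% | 34% | 40% | 24% | 30% |
| 20% v 40% | 16% | 20% | 10% | 13% |

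Across these rows the stricter threshold adds about 3 to 11 percentage points to the miss rate. Most of the miss rate at low base rates comes from the sample size, not from the threshold.

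**5. What an interval would add.** Newcombe 95% CIs at 107 per arm:
- 5 v 5 patients with an event: difference 0, CI −6.4 to +6.4 points. Equal counts at about 5% (5/107 = 4.7%) do not exclude a doubling.
- 10 v 5: difference +4.7 points, CI −2.5 to +12.2.

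Neither interval would appear in Tables 7.1 to 7.4 as drafted.

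**The case against.** The strongest reply is that the SAP already estimates the harms that matter most. Effusion, bleeding, phrenic nerve palsy, PV stenosis, drug side-effects, death and stroke all get a Cox hazard ratio with a 95% CI for both comparisons. This stands, and it limits the point to the overall AE and SAE tables. A reader might infer that no harm in this trial gets an estimate, or that p ≤ 0.025 is the only comparative safety criterion. Tables 5.3 and 5.6 rule that out. Nor does Protocol 6.3 support the wider reading when it says the conventional arm serves "to compare the differences in impact on healthcare resources, complication rates and clinical outcomes between conventional ablation and AVATAR-protocol ablation": complications are the outcome that already has an estimate. What remains is that the complications endpoint counts only events attributed to the procedure or drug. The all-cause AE and SAE totals, which need no attribution, are the ones without an estimate.

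Second, SAP 8.4 is mainly descriptive, tests only where thought appropriate, and mentions a generalized linear model that could yield an estimate. This also stands, but no effect measure or interval is specified and the shells have no place for one.

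Third, a reader might take a miss rate of 80% or more as a property of the design. It depends on the assumed base rate. Protocol 10.5 records every non-serious AE, expected or not, so the proportion with any AE could be well above 5%. At 12% v 24% the chi-square test misses 47%.

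Fourth, an example such as 14 v 5 events (chi-square p = 0.031, 95% CI 0.7 to 16.5 points) might seem to show the rule hiding a clear harm. It mixes two alpha levels: the matching 97.5% CI is −0.6 to 17.8 points, and Fisher gives p = 0.052.

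Finally, the SAP nowhere says that a non-significant result means safe, no current objective claims comparable safety, and a DSMB reviews safety data during the trial.

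**Conclusion.** The point holds for overall AEs and SAEs, and it is minor. SAP 8.4 applies to harms a threshold derived for the primary endpoint, and shells 7.1 to 7.4 contain no between-arm estimate or interval. At 107 per arm, the stricter threshold raises the chance of missing a doubling from 71% to 81% (chi-square) or 79% to 87% (Fisher) at 5% v 10%; from 45% to 57% or 53% to 64% at 10% v 20%; and from 10% to 16% or 13% to 20% at 20% v 40%. These sizes rest on assumed event rates, full follow-up of 107 per arm and two-sided tests. That the interval is missing does not depend on any of these assumptions. The point does not extend to complications or to death or stroke.

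**What to change.** In SAP 8.4:
- Do not apply the 0.025 threshold to AEs and SAEs. Keep it for the two primary-endpoint comparisons.
- For AVATAR v drugs and AVATAR v conventional, report the difference in the proportion of patients with any AE, any SAE and any treatment-related SAE, each with an unadjusted two-sided 95% CI (for example Newcombe). State which causality categories count as treatment-related.
- Add these columns to Tables 7.1, 7.2 and 7.4, following the estimate-plus-interval format that Table 5.6 already has for complications.
- State that a non-significant difference is not evidence of comparable safety.

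The cost is SAP wording and extra columns in three shells, with no new data or patients. The downside is that, without a multiplicity correction, more chance differences in harms will have a 95% CI that excludes zero. The text should say that these intervals are descriptive.

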8.5. Health Economic Analysis

A health economist is to analyse selected data to determine the overall economic benefits of antral AF ablation without electrophysiological confirmation of PV isolation. Details of this analysis will be covered in a separate document, external from the SAP.

8.6. Interim Analysis

Interim reports detailing baseline demographics, safety endpoints and primary endpoints (if requested) will be produced for assessment and discussion at DSMB meetings, the framework of which will be provided within the DSMB charter.

8.7. Tables to Present

Table 1.1: Subject Disposition

	Site A	Site B	...	Total
Screened				
Randomised				
Treatment A				
Treatment B				
Treatment C				
Withdrawn				
Reason for Withdrawal				
Completed				

Table 2.1: Listing of protocol deviations

Treatment	Subject	Site	Type	Start Date	End Date

Table 2.2: Number of protocol deviations by centre and category

Type of Deviation	Site A	Site B	...	Total
Patient was incorrectly included in the trial (did not meet all the inclusion and exclusion criteria)				
:				
Patient pregnancy				
Other				
Total				

Table 3.1: Baseline characteristics

Variable	Statistics	AVATAR-AF Ablation	Anti-arrhythmic therapy	Conventional AF Ablation
Age (y)	N Mean SD Min Median Max			
Race (n (%))	xxxxxx xxxxxx			
Ethnicity (n (%))	xxxxxx xxxxxx			
Gender (n (%))	Female Male			
Height (cm)	N Mean SD Min Median Max			
Weight (kg)	N Mean SD Min Median Max			
Pulse (bpm)	N Mean SD Min Median Max			
Systolic BP	N Mean			

	SD	
	Min	
	Median	
	Max	
Diastolic BP	N	
	Mean	
	SD	
	Min	
	Median	
	Max	
QoL Score	N	
	Mean	
	SD	
	Min	
	Median	
	Max	
QoL Score (n (%))	<40	
	...	
	90-99	
	100+	
Chadsvasc Score (n (%))	0	
	1	
	..	
	6	
AFEQT Score	N	
	Mean	
	SD	
	Min	
	Median	
	Max	
AFEQT Score (n (%))	0-19	
	...	
	80-100	

Anti-Arrhythmics Taken (n (%))	Amiodarone	
	...	
	Propafenone	
Beta Blockers Taken (n (%))	xxxxx	
Calc. Ch. Blocker Taken (n (%))	xxxxx	
Record of Anti-Coag Pre-Procedure (n (%))	Yes – Bridging	
	Yes – Continuous	
	No	
Expectation of Anti-Coag Post-Procedure (n (%))	Yes	
	No	
Subjects displaying evidence of Paroxysmal Atrial Fibrillation (n (%))	Yes	
	No	
ECG Rhythm (n (%))	Sinus	
	SVT	
	...	
	Q-Waves	
Ejection Fraction (%)	N	
	Mean	
	SD	
	Min	
	Median	
	Max	
Pericardial Effusion (n (%))	Yes	
	No	
Presence of Thrombus (n (%))	Yes	
	No	

***Table Note: To include the following variables - Age, race, ethnicity, gender, height, weight, pulse rate, Systolic BP, Diastolic BP, QoL Score, AFEQT Score, CHADSVASC Score, Heart Medications Taken, Record of Anti-Coagulation pre-procedure, Anti-Coagulation requirements post-procedure 24hr Holter, ECG, Echocardiology.**

PRIMARY ENDPOINT

Table 4.1: Listing of all hospital episodes (Emergency Room or patient request for OPD) related to treatment for atrial arrhythmia.

Treatment	Subj.	Date of Visit	Discharge Protocol?	Reason for Adjudication	Outcome	Endpoint?	Time to Event

Table 4.2: Log-rank test investigating occurrence of AF related hospital visits*

Treatment Arm	Events Observed	Events Expected
Total		

Chi2(1) = x.xxx

Pr>chi2 = 0.xxx

*4.2.1 – Comparison between AVATAR-AF and Anti- Arrhythmics

*4.2.2 – Comparison between AVATAR-AF and Conventional Ablation

Table 4.3: Cox proportional hazards model investigating occurrence of AF related hospital visits*

Variable	Obvs	Mean	SD	Min	Max
Time to Endpoint	xxx	xx.x	xx.xx	xx	xx
Endpoint Occurred	xxx				
Treatment	xxx				
_st	xxx				
_d	xxx				
_t	xxx				
_t0	xxx				

_t	Haz. Ratio	SE	z	P> z	95% CI
Treatment	x.xxx	x.xxx	x.xx	0.xxx	x.xxx x.xxx

*4.3.1 – Comparison between AVATAR-AF and Anti- Arrhythmics

*4.3.2 – Comparison between AVATAR-AF and Conventional Ablation

SECONDARY ENDPOINTS

Table 5.1: Listing of deaths or strokes from any cause.

Treatment Arm	Subject Number	Type of Event	Date/Time of Event	Time to Event	Cause of Event	Relation to Treatment	Comments

Table 5.2: Log-rank test investigating occurrence of deaths and strokes*

Treatment Arm	Events Observed	Events Expected
Total		

Chi2(1) = x.xxx

Pr>chi2 = 0.xxx

*5.2.1 – Comparison between AVATAR-AF and Anti- Arrhythmics

*5.2.2 – Comparison between AVATAR-AF and Conventional Ablation

Table 5.3: Cox proportional hazards model investigating occurrence of deaths and strokes*

Variable	Obvs	Mean	SD	Min	Max
Time to Endpoint	xxx	xx.x	xx.xx	xx	xx
Endpoint Occurred	xxx				
Treatment	xxx				
_st	xxx				
_d	xxx				
_t	xxx				
_t0	xxx				

_t	Haz. Ratio	SE	z	P> z	95% CI
Treatment	x.xxx	x.xxx	x.xx	0.xxx	x.xxx x.xxx

*5.3.1 – Comparison between AVATAR-AF and Anti- Arrhythmics

*5.3.2 – Comparison between AVATAR-AF and Conventional Ablation

Table 5.4: Listing of complications arising from therapy.

Treatment Arm	Subject Number	Type of Event	Date/Time of Event	Time to Event	Cause of Event	Relation to Treatment	Comments

Table 5.5: Log-rank test investigating occurrence of complications*

Treatment Arm	Events Observed	Events Expected
Total		

Chi2(1) = x.xxx

Pr>chi2 = 0.xxx

*5.5.1 – Comparison between AVATAR-AF and Anti- Arrhythmics

*5.5.2 – Comparison between AVATAR-AF and Conventional Ablation

Table 5.6: Cox proportional hazards model investigating occurrence of complications*

Variable	Obvs	Mean	SD	Min	Max
Time to Endpoint	xxx	xx.x	xx.xx	xx	xx
Endpoint Occured	xxx				
Treatment	xxx				
_st	xxx				
_d	xxx				
_t	xxx				
_t0	xxx				
_t	Haz. Ratio	SE	z	P> z	95% CI
Treatment	x.xxx	x.xxx	x.xx	0.xxx	x.xxx x.xxx

*5.6.1 – Comparison between AVATAR-AF and Anti- Arrhythmics

*5.6.2 – Comparison between AVATAR-AF and Conventional Ablation

Table 5.7: Listing of hospital episodes resulting in a change in therapy for atrial arrhythmia

Treatment Arm	Subject Number	Type of Event	Date/Time of Event	Time to Event	Cause of Event	Relation to Treatment	Comments

Table 5.8: Log-rank test investigating occurrence of hospital episodes resulting in a change in therapy for atrial arrhythmia*

Treatment Arm	Events Observed	Events Expected
Total		

Chi2(1) = x.xxx

Pr>chi2 = 0.xxx

*5.8.1 – Comparison between AVATAR-AF and Anti- Arrhythmics

*5.8.2 – Comparison between AVATAR-AF and Conventional Ablation

Table 5.9: Cox proportional hazards model investigating occurrence of hospital episodes resulting in a change in therapy for atrial arrhythmia*

Variable	Obvs	Mean	SD	Min	Max
Time to Endpoint	xxx	xx.x	xx.xx	xx	xx
Endpoint Occured	xxx				
Treatment	xxx				
_st	xxx				
_d	xxx				
_t	xxx				
_t0	xxx				
_t	Haz. Ratio	SE	z	P> z	95% CI
Treatment	x.xxx	x.xxx	x.xx	0.xxx	x.xxx x.xxx

*5.9.1 – Comparison between AVATAR-AF and Anti- Arrhythmics

*5.9.2 – Comparison between AVATAR-AF and Conventional Ablation

SAFETY AND EFFICACY – TREATMENT PROCEDURE

Table 6.1: Summary of 1st Intervention (Both Ablation Arms)

Variable	Statistics	AVATAR-AF Ablation	Conventional AF Ablation
CHADSVASC Score	N Mean SD Min Median Max		
No. Subjects Anti-Coagulated pre-procedure	Yes – Bridging Protocol Yes – Cont. Protocol No Yes No		
No. Subjects Anti-Coagulated post-procedure	Yes No		
Was TOE performed	Yes No		
Sedation Type	GA Sedation +/- Local Local Only		
Transseptal Puncture Method	Transoesophageal Echo Aortic pigtail Coronary Sinus Catheter Intracardiac Echo		
Diaphragmatic Monitoring Method	Visual Only Phrenic Nerve Pacing w/ Temp Box Phrenic Nerve Pacing w/ EP Stimulator Other Phrenic Nerve Monitoring		
RLPV Lowest Temperature Recorded	N Mean SD Min Median Max		
RUPV Lowest Temperature Recorded	N Mean SD		

	Min	
LUPV Lowest Temperature Recorded	Median	
	Max	
	N	
	Mean	
	SD	
	Min	
	Median	
LLPV Lowest Temperature Recorded	Max	
	N	
	Mean	
	SD	
	Min	
	Median	
RLPV PV Isolation after Adv. Balloon Alone?	Max	
	Yes	
	No	
RUPV PV Isolation after Adv. Balloon Alone?	Yes	
	No	
LUPV PV Isolation after Adv. Balloon Alone?	Yes	
	No	
LLPV PV Isolation after Adv. Balloon Alone?	Yes	
	No	
RLPV Complete (Grade 4) Occlusion Achieved?	Yes	
	No	
RUPV Complete (Grade 4) Occlusion Achieved?	Yes	
	No	
LUPV Complete (Grade 4) Occlusion Achieved?	Yes	
	No	
LLPV Complete (Grade 4) Occlusion Achieved?	Yes	
	No	
All Veins Isolated at end of procedure?	Yes	
	No	
Diaphragmatic Motion Normal at end of procedure?	Yes	
	No	
Patient Fully Anti-Coagulated on Discharge?	Yes	
	No	
Daycase Discharge?	Yes	
	No	

Table 6.2: Summary of Week 8 Review (Both Ablation Arms)

Variable	Statistics	AVATAR-AF Ablation	Conventional AF Ablation
Status of Patient at Review	Asymptomatic for palpitations Showing weekly improvement Not possible to assess in time scale Experiencing ongoing symptoms		
No. Patients referred for Re-Do Procedure	Yes No		

Table 6.3: Summary of 2nd Intervention (Both Ablation Arms)

Variable	Statistics	AVATAR-AF Ablation	Conventional AF Ablation
CHADSVASC Score	N Mean SD Min Median Max		
No. Subjects Anti-Coagulated pre-procedure	Yes – Bridging Protocol Yes – Cont. Protocol No		
No. Subjects Anti-Coagulated post-procedure	Yes No		
Was TOE performed	Yes No		
:			
LUPV Isolation at Start?	Yes No		
LLPV Isolation at Start?	Yes No		
RUPV Isolation at Start?	Yes No		
RLPV Isolation at Start?	Yes No		

Table 6.4: Summary of 1st Intervention (Anti-Arrhythmic Arm)

Variable	Statistics	Anti-arrhythmic therapy
Number of Subjects	N	
Anti-Arrhythmic Assigned (%)	Amiodarone Dronedarone Sotalol Digoxin Flecainide ⋮	
Beta-Blocker Assigned (%)	Atenolol Bisoprolol Metoprolol Propanolol ⋮	

